### **9.4.1 General Considerations**

Statistical analyses will be primarily descriptive in nature. All tabulations, figures, and listings will be produced using the Statistical Analysis Software (SAS) System (Version 9.2 or higher). Data from all participating sites will be pooled for analysis. Standard method of imputation will be applied for any missing/ partial dates.

According to the objectives, the relevant parameters will be summarised descriptively with appropriate statistical methods: categorical variables will be presented using frequencies, percentages and corresponding 95% CI (using Clopper-Pearson exact method, where appropriate) and continuous variables using number of observations, arithmetic mean, standard deviation (SD), median, 25th and 75th percentiles, and minimum and maximum values. The last measurement prior to first dose of study treatment will serve as the baseline measurement.

The safety parameters including AEs, SAEs, deaths, treatment discontinuation/modification, patient discontinuation, laboratory data, etc. will be reported using safety analysis set.

The time-to-event endpoint will be summarised using Kaplan-Meier (KM) method along with the corresponding 95% CIs (as appropriate) and the KM curve will be plotted.

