## 9.4.2 Safety

### 9.4.2.1 Primary Endpoints

In order to assess safety and tolerability of benralizumab in participants with severe eosinophilic asthma, following results will be presented:

Frequency, percentage, and 95% CIs (using Clopper-Pearson exact method) will be reported for the following:

- AEs
- SAEs
- TEAEs
- Participants with unexpected Adverse Drug Reactions (ADRs)
- Participants with AEs that lead to study treatment discontinuations or modifications.

The AE profiles in participants will be presented as summaries showing the number of participants (n, %) along with number of events by System Organ Class and Preferred Terms assigned to the event by Medical Dictionary for Regulatory Activities (MedDRA) for the following:

- TEAEs
- SAEs
- Related and non-related TEAEs
- Serious and non-serious TEAEs
- TEAEs based on severity (Mild, Moderate, Severe)
- Unexpected ADRs based on severity (Mild, Moderate, Severe)

The physical examination, vital signs, and laboratory parameters (if available) will be summarised descriptively for actual values and change from baseline values for each visit using the number of observations, arithmetic mean, SD, median, 25th and 75th percentiles, and minimum and maximum values.

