1. INTRODUCTION

The purpose of this document is to provide a description of the statistical methods and procedures to be implemented for the analysis of data from D3250C00093 study. This document is based on protocol V 1.0, 09 Mar 2021. The statistical planning and conduct of analysis of the data from this study will follow the principles defined in relevant International Council on Harmonisation (ICH)-E9 guidelines. Any change from the planned analysis as described in the protocol, are detailed here, and any differences described here supersede the analysis as presented in the protocol.

2. Study Objective and Design

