6.2 Efficacy Hypothesis

There is no statistical hypothesis to be tested in this study.

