6.3.1 Primary Endpoint Analysis

The primary analysis for primary endpoint will be based on Safety Analysis Set.

Primary Endpoint evaluations will include Adverse Events (AEs), Serious Adverse Events (AEs), Treatment Emergent Adverse Event (TEAEs), Participants with unexpected Adverse Drug Reactions (ADRs) and Participants with AEs that lead to study treatment discontinuations or modifications.

Adverse Events (AEs), Serious Adverse Events (AEs), Treatment Emergent Adverse Event (TEAEs), Participants with unexpected Adverse Drug Reactions (ADRs) and Participants with AEs that lead to study treatment discontinuations or modifications will be summarized using Frequency, Percentages and 95% CIs (using Clopper-Pearson Exact method).

Document Title:	Document ID:	BP04-01
Statistical Analysis Plan	Version Number:	3.1
	Effective Date:	25-Nov-2021

The AE profiles in participants will be presented as summaries showing the number of participants (n, %) along with number of events by System Organ Class and Preferred Terms assigned to the event by Medical Dictionary for Regulatory Activities (MedDRA) for the following:

- TEAEs
- SAEs
- Related and non-related TEAEs
- Serious and non-serious TEAEs
- TEAEs based on severity (Mild, Moderate, Severe)
- Unexpected ADRs based on severity (Mild, Moderate, Severe)

Physical Examination will include General Appearance, Respiratory system, Cardiovascular system, Abdomen, Skin, Head, Eye, Ear, Nose, Throat, Lymph node, Thyroid, Musculoskeletal system and Neurological System. Physical Examination will be summarized based on the Safety Analysis Set.

Descriptive summaries will be provided for the Physical Examination.

All the continuous variables will be summarized by n, mean, standard deviation, minimum, median and maximum values. All the categorical variables will be summarized as frequency, percentage of Patients in each category and corresponding 95% CI (using Clopper-Pearson exact Method, where appropriate).

Vital Signs will include Pulse rate, Respiratory rate, Systolic Blood Pressure, Diastolic Blood Pressure and Temperature.

Vital Signs will be summarized based on the Safety Analysis Set.

Vital Signs will be summarised descriptively for actual values and change from baseline values for each visit using the number of observations, arithmetic mean, SD, median, 25th and 75th percentiles, and minimum and maximum values.

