The Vital signs (Pulse rate, Respiratory rate, Systolic Blood Pressure, Diastolic Blood Pressure and Temperature) in this study is to evaluate the change from baseline to Post-baseline will be analysed using Paired t – test / Wilcoxon signed-rank test at 5% level of significance.

Change from baseline will be determined as:

Change from Baseline = (Post-baseline – Baseline)

Percent Change Change from Baseline = ([Post-baseline – Baseline] / Baseline) X 100

Clinical Safety laboratory Assessment will include clinical chemistry, haematology and urinalysis. Clinical Safety laboratory assessment will be summarized based on the Safety Analysis Set.

Document Title:	Document ID:	BP04-01
Statistical Analysis Plan	Version Number:	3.1
	Effective Date:	25-Nov-2021

Clinical Safety laboratory Assessment will be summarised descriptively for actual values and change from baseline values for each visit using the number of observations, arithmetic mean, SD, median, 25th and 75th percentiles, and minimum and maximum values.

The Clinical Safety Laboratory (If available) in this study is to evaluate the change from baseline to Post-baseline will be analysed using Paired t – test / Wilcoxon signed-rank test at 5% level of significance.

Change from baseline will be determined as:

Change from Baseline = (Post-baseline – Baseline)

Percent Change Change from Baseline = ([Post-baseline – Baseline] / Baseline) X 100

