- n = number of Patients in row category; E = number of serious TEAE
- TEAE are those adverse events which occurred after first dose of study medication.
- All Percentages rows are based on the total number of patients in the Safety Analysis Set.
- System Organ classes was sorted by descending frequency. Preferred terms are sorted by descending frequency within system organ class.
- Adverse events were coded using MedDRA version 24.1 If a patient has multiple occurrences of an AE, the patient is presented only once in the respective patient count column (n) for the corresponding AE. Events are counted each time in the event € column.
- Source: Listing 16.3.1.2, Listing 16.3.2.1 and Listing 16.3.2.2

Document Title:	Document ID:	BP04-01
Statistical Analysis Plan	Version Number:	3.1
	Effective Date:	25-Nov-2021

Table 14.3.3. Analysis of change in Vital Sign parameters from baseline to Visit 1, Visit 2, Visit 3, Visit 4 and Visit 5 (Safety Analysis Set)

	Observed value (N = xx)	Change from Baseline (N = xx)	% Change from Baseline (N = xx)
Vital Sign parameter x			
Baseline (Screening Visit)			
n	xx		
Missing	xx		
Mean (SD)	xx.x (xx.xx)		
Median	xx.x		
(min, max)	(xx.xx, xx.xx)		
(25 th percentiles, 75 th percentiles)	(xx.xx, xx.xx)		
Visit x			
n	Xx	Xx	xx
Missing	Xx	Xx	Xx
Mean (SD)	xx.x (xx.xx)	xx.x (xx.xx)	xx.x (xx.xx)
Median	xx.x	xx.x	xx.x
(min, max)	(xx.xx, xx.xx)	(xx.xx, xx.xx)	(xx.xx, xx.xx)
(25 th percentiles, 75 th percentiles)	(xx.xx, xx.xx)	(xx.xx, xx.xx)	(xx.xx, xx.xx)
p-value		x.XXX	x.XXX

- The Capital "N" in the column header represents the total number of patients in Safety Analysis Set.
- The small "n" in summary statistics represents the total number of patients.
- SD = Standard deviation, min=minimum, max=maximum
- Change from Baseline= Post-Baseline – Baseline
- % Change from Baseline = (Post-Baseline – Baseline / Baseline) X 100
- p-value calculate using paired t – test.
- Programmer Note: Vital Signs parameter x: Pulse rate (beats/min), Respiratory rate (breaths/min), Systolic blood pressure (mmHg), Diastolic blood pressure (mmHg) and Temperature(⁰F).
- Programmer Note: Visit x: Visit 1, Visit 2, Visit 3, Visit 4 and Visit 5
- Source: Listing 16.3.4

Document Title:	Document ID:	BP04-01
Statistical Analysis Plan	Version Number:	3.1
	Effective Date:	25-Nov-2021

(25th percentiles, 75th percentiles)

(xx.xx, xx.xx)

- The Capital "N" in the column header represents the total number of patients in Safety Analysis Set.

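### SAP 6.3.1 adds 39 to 43 unadjusted 5%-level paired tests on vital-sign and laboratory changes to a study that says it tests no hypothesis

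*SAP*

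**What the plan says.** Protocol 9.1 and SAP 6.2 carry the same sentence: "There is no statistical hypothesis to be tested in this study". Protocol 9.4.1 adds: "Statistical analyses will be primarily descriptive in nature". For vital signs and laboratory parameters, Protocol 9.4.2.1 plans that they "will be summarised descriptively for actual values and change from baseline values for each visit", and names no test.

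SAP 6.3.1 repeats those summaries. It then says that change from baseline in vital signs, and separately in the clinical safety laboratory values, will be analysed by paired t-test or "Wilcoxon signed-rank test at 5% level of significance". It has no rule for choosing between the two tests, no multiplicity adjustment and no exploratory label. SAP section 1 says that changes from the protocol analysis are detailed in the SAP and that "any differences described here supersede the analysis as presented in the protocol". The tests are not identified as such a change, but this clause makes them operative.

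The scope comes from the text and the shell. SAP 6.3.1 states: "Vital Signs will include Pulse rate, Respiratory rate, Systolic Blood Pressure, Diastolic Blood Pressure and Temperature". The shell for Table 14.3.3 takes the screening visit as baseline and instructs: "Programmer Note: Visit x: Visit 1, Visit 2, Visit 3, Visit 4 and Visit 5". It prints one p-value for change and another for percentage change, with the footnote "p-value calculate using paired t – test".

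**The concern.** A test at a stated significance level is a hypothesis test, so the SAP does what both documents say the study does not do. With dozens of such tests and no adjustment, some will probably cross 5% by chance.

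The study has one arm and exists to provide safety data for a post-approval commitment. A p-value on mean change cannot separate a drug effect from the passage of time, and it says nothing about individual patients with large shifts. A small p-value could be reported as a safety signal. A large one could be read as evidence that the measurement is unaffected, which it is not.

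**Working it through.** **The plan's own figure.** The documents state no error rate for these tests. Their only sizing figure is 139 evaluable and 147 enrolled, and it reproduces:

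- n = z²p(1−p)/d² = 1.96² × 0.10 × 0.90 / 0.05² = 138.3, rounded up to 139
- 139 / 0.95 = 146.3, rounded up to 147

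That calculation fixes the precision of an adverse-event proportion. It neither sizes nor controls tests on mean change.

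**Counting the tests on absolute change.**

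- Vital signs: 5 parameters (SAP 6.3.1) × 5 visits (Table 14.3.3) = 25.
- Chemistry: 9 analytes (Protocol 8.1.3) × 1 post-baseline time point (Week 24) = 9.
- Haematology: 5 items if the differential counts as one, or 4 + 5 = 9 if it is reported as five cell types (an assumption), × 1 time point.
- Dipstick urinalysis is left out, because no change table is listed for it.

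The total is 25 + 9 + 5 = 39 to 25 + 9 + 9 = 43. The laboratory shells (Tables 14.3.2.1 and 14.3.2.2) are listed but not visible, so these tests are counted from the text of SAP 6.3.1. The eosinophil tests planned as a secondary endpoint in SAP 6.3.2 are not counted.

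**Error if nothing truly changes.** Two-sided 5% tests are assumed, as sidedness is not stated. The expected number of false positives is 0.05k. Under independence, P(at least one) = 1 − 0.95^k.

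| Tests counted | k | Expected | P(at least one) |
|---|---|---|---|
| All, differential as one item | 39 | 1.95 | 86.5% |
| All, five cell types | 43 | 2.15 | 89.0% |
| As k = 43, without eosinophils | 42 | 2.10 | 88.4% |
| As k = 39, without Visit 1 | 34 | 1.70 | 82.5% |
| As k = 43, without Visit 1 | 38 | 1.90 | 85.8% |

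**Allowing for correlation.** Independence cannot hold: each vital sign is tested five times in the same patients against one baseline. A multivariate normal simulation under the global null (200,000 runs per setting) used assumed correlations, since the documents give none.

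| Between visits / between vital signs / between laboratory values | k = 39 | k = 43 |
|---|---|---|
| 0.5 / 0 / 0 | 82% | 86% |
| 0.7 / 0.3 / 0.3 | 73% | 76% |
| 0.8 / 0.5 / 0.5 | 61% | 64% |

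The expected number stays at about two in every setting.

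**The Visit 1 comparison.** Visit 1 is Day 1, and the Schedule of Activities and Protocol 8.1.2 have vital signs taken before dosing. Table 14.3.3 therefore compares screening with a second pre-treatment value. Its 5 tests cannot show a drug effect, yet under independence they carry a 1 − 0.95⁵ = 22.6% chance of at least one p-value below 5%. Protocol 9.4.1 takes the last measurement before the first dose as baseline. On that rule a recorded pre-dose Day 1 value is itself the baseline, so the shell and the protocol disagree.

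**The case against.** The strongest reply is that little depends on these p-values. The primary adverse-event endpoints are not tested; they get frequencies, percentages and Clopper-Pearson intervals. Clinically relevant deterioration in laboratory values or vital signs is to be reported as an adverse event (Protocol 8.1.2 and 8.2.3), so individual harm has its own route into the primary analysis. The protocol says its analyses are primarily, not wholly, descriptive. The SAP's no-hypothesis sentence sits under an efficacy heading, and SAP 5.2 sets a format for p-values. All of this stands and limits the harm, but it does not remove the conflict: the sentence covers the whole study, and the tests have a 5% threshold and no label.

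A reader might also infer more than the documents support:

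- *That false findings are almost certain.* This would need independence, or counting the percentage-change p-values as separate tests. Doing the latter, and assuming that the laboratory shells have the same columns, gives k = 78 to 86 and 98.2% to 98.8%. Change and percentage change are nearly the same test, so those figures overstate the risk.
- *That every significant result would be false.* The protocol expects near-complete eosinophil depletion, so a significant fall in that count would be a real effect.
- *That dipstick results will be given t-tests.* The wording of SAP 6.3.1 does include urinalysis, but the planned outputs contain only a urinalysis listing, with no summary or change table.
- *That the test can be chosen after seeing the data.* Table 14.3.3 fixes the t-test for vital signs; on the visible text only the laboratory choice is open. The disposition counts printed under Table 14.1.1.1 do not show that vital-sign or laboratory results had been seen, and Protocol 9.4 allows the SAP to be finalised up to database lock.

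**Conclusion.** The point holds as a reporting defect that should be corrected. Followed as written, the SAP is likely to produce at least one spurious significant safety change, with about two expected if nothing truly changes. The probability is roughly 60% to 90%, depending on correlation. This rests on two-sided tests, a count of 39 to 43 that varies with the reporting of the differential, correlations that are assumed, and laboratory tests read from the SAP text. It does not inflate the error of any primary endpoint or trial-level decision. The screening baseline and the Visit 1 tests in Table 14.3.3 need correcting whatever is decided about the p-values.

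**What to change.** - Delete the paired tests and p-values for vital signs and laboratory values from SAP 6.3.1 and from the shells.
- Report mean or median change with a 95% CI from the last pre-dose value, and drop Visit 1 as a post-baseline visit. The intervals should be read as estimates: scanning them for those that exclude zero would bring back the same multiplicity.
- Tabulate by visit the normal/abnormal and clinical-significance flags already held in the laboratory and vital-sign listings. Table 14.3.5 does this for the physical examination and can serve as the format.
- Limit the urinalysis wording in SAP 6.3.1 to categorical summaries or listings, to match the planned outputs.
- If any p-value is kept, label it exploratory, name one test in advance, and declare it as a change from the protocol.

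The cost is SAP wording and shell edits, with no new data. What is lost is a set of p-values that the protocol never planned.

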### **8.1.3 Clinical Safety Laboratory Assessments**

Blood and urine samples for determination of clinical chemistry, haematology, and urinalysis will be collected at screening and at EOS (Day 168±7) as indicated in the SoA.

Clinical chemistry will include serum alkaline phosphatase, alanine aminotransferase, aspartate aminotransferase, gamma glutamyl transferase, lactate dehydrogenase, total protein, total bilirubin, albumin, and serum creatinine. Haematology will include haematocrit, leucocyte count, leucocyte differential count (absolute count), platelet count, and haemoglobin. Urinalysis (dipstick) will assess urine haemoglobin/erythrocytes/blood, protein/albumin, and glucose.

Additional safety samples may be collected if clinically indicated at the discretion of the investigator. The date, time of collection, and results (values, units, and reference ranges) will be recorded on the appropriate eCRF.

The clinical chemistry, haematology, and urinalysis will be performed at a local laboratory at or near the investigator site. Sample tubes may vary depending on laboratory method used and routine practice at the site.

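### SAP 6.3.1 applies a continuous-data method to dipstick urinalysis, lists no urinalysis table, and shows no planned tabulation of normal-to-abnormal laboratory shifts

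*SAP*

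**What the plan says.** SAP section 6.3.1 treats the three laboratory domains together: "Clinical Safety laboratory Assessment will include clinical chemistry, haematology and urinalysis". They are to be "summarised descriptively for actual values and change from baseline values for each visit using the number of observations, arithmetic mean, SD, median", with quartiles, minimum and maximum added. The "change from baseline to Post-baseline will be analysed using Paired t – test / Wilcoxon signed-rank test at 5% level of significance", and the section supplies the formula "Percent Change Change from Baseline = ([Post-baseline – Baseline] / Baseline) X 100". No separate method is given for urinalysis, and no rule for choosing between the two tests.

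Protocol section 8.1.3 describes the measurement: "Urinalysis (dipstick) will assess urine haemoglobin/erythrocytes/blood, protein/albumin, and glucose". It also says that all laboratory work "will be performed at a local laboratory at or near the investigator site", with sampling planned at screening and at Week 24. Results are recorded in the eCRF with units and reference ranges. Protocol section 9.4.1 pools the sites.

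Among its laboratory summaries the SAP's table list has Table 14.3.2.1 (haematology change) and Table 14.3.2.2 (biochemistry change), then moves to vital signs. Urinalysis appears as Listing 16.3.3.3 only. Listings 16.3.3.1 to 16.3.3.3 show, for each patient and visit, the result, the reference range, a normal/abnormal call and a clinical-significance (CS/NCS) flag.

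**The concern.** There are two linked problems.

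First, dipstick blood, protein and glucose are graded categories. A mean or SD of such grades depends on an arbitrary scoring, and percent change has a zero denominator for a negative baseline scored zero. One of the three laboratory domains is therefore assigned a method that does not fit it, while the output list gives it no summary table at all. A programmer could not satisfy both the text and the list.

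Second, laboratory safety is mainly about individual patients crossing a limit. For chemistry and haematology the visible plan is an analysis of change, with no count of patients who were normal at baseline and abnormal at Week 24. Protocol section 8.2.3 limits which deteriorations become adverse events, having said that laboratory results will be summarised in the study report. The shifts that stay outside the AE tables therefore depend on that summary to be seen, in a study whose primary objective is safety.

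**Working it through.** **1. Figures in the plan.** The documents give no figure for the laboratory analysis, so there is none to reproduce. The patient numbers used below come from the footnote to SAP Table 14.1.1.1: 154 screened − 10 screen failures − 6 untreated = 138 in the analysis set; 124 completed the study.

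**2. The stated method against a dipstick result.**

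| Element of SAP 6.3.1 | Applied to dipstick grades |
|---|---|
| Mean, SD | Depend on the score given to each grade; no scoring is specified |
| Percent change | (post − 0)/0 for a negative baseline scored 0: undefined |
| Paired t-test | Treats the steps between grades as equal distances |
| Wilcoxon signed-rank | Closer to ordinal data, but still ranks numerical differences between grades, and tests net direction only |

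**3. Net change hides two-way movement (assumed data).** Score negative = 0 and positive = 1 in 138 patients. Let k patients go from negative to positive and k from positive to negative, the rest staying negative.
- Mean change = (k × 1 − k × 1)/138 = 0, so t = 0 and p = 1.00, for k = 1, 3, 5 or 10.
- The positive and negative signed ranks are equal by symmetry, so the Wilcoxon test is no more informative.
- Patients with baseline 0 number 138 − k: 137/138 = 99.3% for k = 1, and 128/138 = 92.8% for k = 10. Percent change is undefined for all of them.
- Yet k patients have developed an abnormality.

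**4. Text against outputs.** The text names urinalysis as analysed. The table list has no urinalysis table, and Listing 16.3.3.3 is its only output. By contrast, SAP Table 14.3.5 tabulates physical examination as normal, abnormal CS and abnormal NCS. The SAP therefore already uses this kind of count, but not visibly for laboratory data.

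**5. Chemistry: mean change does not give a patient count (assumed data).** Suppose 3 of the 124 completers have ALT rising from 30 to 150 U/L and the others do not change.
- Mean change = 3 × 120/124 = 2.9 U/L.
- Patients shifting = 3/124 = 2.4%.

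A simulation assumed N = 138, baseline mean 25 and SD 7, within-patient change SD 7, and k patients rising by 100 U/L.

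| k | Mean change (U/L) | Paired t-test p < 0.05 |
|---|---|---|
| 3 | about 2.2 | 18% of simulations |
| 5 | about 3.6 | 67% |
| 7 | about 5.1 | 98% |

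The test may or may not react, and in neither case does it report k.

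**6. What a shift table would report.** Exact Clopper-Pearson 95% intervals, assuming every patient is normal at baseline and measured at Week 24:

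| Shifts | N = 138 | N = 124 |
|---|---|---|
| 0 | 0% (0 to 2.64%) | 0% (0 to 2.93%) |
| 3 | 2.17% (0.45 to 6.22%) | 2.42% (0.50 to 6.91%) |
| 5 | 3.62% (1.19 to 8.25%) | 4.03% (1.32 to 9.16%) |

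Real denominators will be smaller wherever patients are already abnormal at baseline.

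**The case against.** The case on the other side is substantial.

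- **The counts can be made.** Listings 16.3.3.1 to 16.3.3.3 carry reference range, abnormality call and CS/NCS flag per patient. This stands: what is missing is a planned tabulation, not the information.
- **Important rises become adverse events.** Under protocol section 8.2.3, a deterioration that meets a seriousness criterion, leads to stopping the drug, or is judged clinically relevant is reported as an AE and counted. This stands for those events. It leaves uncounted the shifts that the investigator does not judge relevant.
- **The mean is not alone.** Minimum and maximum are also planned, so a value of 150 U/L would show in the maximum unless another patient's were higher. This stands, but an extreme value is still not a count of patients.
- **A general categorical rule exists.** SAP sections 5.1 and 6.3 summarise categorical variables by frequency and percentage. This helps only partly. The laboratory paragraph is the more specific one and names urinalysis, whereas the physical-examination text in the same section restates the categorical rule. No listed table would carry a urinalysis summary either way.
- **No dipstick p-value table is listed, and Wilcoxon is named.** Both true. The first exposes the conflict between text and outputs; the second does not rescue means or percent change.
- **Table shells.** Those for Tables 14.3.2.1 and 14.3.2.2 are not in the text available, so normal/abnormal rows there cannot be excluded. Their titles mention only change.
- **Pooling of local laboratories.** Within-patient change cancels a constant laboratory offset if the patient uses the same laboratory twice. No mixed units or method differences are shown.
- **Status.** Laboratory values are not among the listed primary endpoints, and no hypothesis is tested. This limits the weight of the point.

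**Conclusion.** The point holds in a limited form. The method that SAP 6.3.1 states for urinalysis is unsuitable for all three dipstick parameters, and the table list does not agree with the text. For every laboratory domain, no normal-to-abnormal tabulation is visible in the SAP text or table titles. For chemistry and haematology this depends on what the two unseen shells contain; for urinalysis it does not.

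Three stronger conclusions might be inferred, and the documents do not support them:
- That the study cannot show how many patients developed an abnormality. The flags are in the listings, and clinically relevant deteriorations reach the AE tables.
- That dipstick t-tests will be reported. The output list contains none.
- That pooling local-laboratory values invalidates the analysis of change. A constant offset cancels within patient.

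The effect on this trial cannot be quantified, because no laboratory distributions are given. The dipstick and ALT examples rest on assumed values and show only the mechanism. The listed primary endpoint analyses and the sample size are unaffected.

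**What to change.** In SAP section 6.3.1:

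1. Give urinalysis its own paragraph. Remove means, percent change and paired tests for dipstick results, and replace them with a baseline-by-Week 24 shift table of dipstick category for blood, protein and glucose. Add this table to the table list.
2. For chemistry and haematology, add low/normal/high shift tables against the recorded local reference range, with the CS/NCS flag, as n and % with Clopper-Pearson 95% CI. State the denominator, for example patients normal at baseline with a Week 24 value. If Tables 14.3.2.1 and 14.3.2.2 already contain such rows, say so in the text instead.

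Expressing enzymes as multiples of the local upper limit is optional.

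The cost is a few extra tables. With two planned sampling times, each is a single cross-tabulation of data already in the eCRF and listings, with no new data collection and no change to the protocol's assessments.
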